### 5 Planned Statistical Methods

If nothing else is stated, all tables, figures and listings will be presented by treatment group (i.e., A1, A2, B1, B2, ..., F2), and will be reported by actual received treatment for the SAF. A subject who receives more or less of the treatment than intended, will be presented in the cohort they belong to. If any subjects receive incorrect treatment, they will be presented separately.

#### 5.1 Statistical Considerations

Baseline is defined as the last assessment with available data prior to the first administration of trial medication. Day 0 is the day of first administration with IMP. Assessments from scheduled visits will be presented when available, otherwise the first unscheduled visit succeeding the scheduled visit in question is used.

Categorical data will be summarized by treatment group, using number and percentages of subjects. For calculation of percentages the denominator will either be the number of subjects in the analysis set or the number of subjects in the analysis set with non-missing values. Continuous data will be presented using the number of subjects (n), mean, standard deviation (SD), median, minimum, and maximum if nothing else is stated. Both the absolute values and the change from baseline will be presented.

Descriptive statistics for all endpoints will be presented by treatment group and visit (if applicable) using observed cases, i.e., no imputation of missing data will be performed.

All statistical tests will be two-sided and performed on a 5 % significance level. Estimated treatment differences and 95 % confidence intervals (CI) will be presented together with the corresponding p-value.

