8.2 Trial procedures

At V1 (Day -90 to -1), the volunteers' eligibility is assessed according to the pre-specified inclusion/exclusion criteria and the informed consent is obtained. The medical history, vital signs (including BMI) are taken, physical and eye examinations are performed. Refer to Table 3 for eye examination method required at V1. Concomitant medications (CM) and AEs are recorded. Blood samples for screening of hepatitis B and C, HIV, syphilis and safety biochemistry/haematology are drawn. Urine is collected for pregnancy test and PCR for *C. Trachoma* and gonorrhoea infections.

At V2 (Day 0), the inclusion/exclusion criteria are assessed again. Eye and symptom-direct physical examination are performed and vital signs are taken. Refer to Table 3 for eye examination method required at V2. Any AEs and CMs are reviewed and recorded. Urine is collected for pregnancy test. The volunteers are randomised according to the randomisation scheme via the eCRF. Before the 1st IM vaccination, blood samples for safety and immunogenicity determination (please refer to type of tests in Table 4) are drawn and ocular samples are taken. The volunteers (hereafter subjects) receive the 1st IM vaccination. The subjects are observed for any immediate AE for 60 minutes after the vaccination. The diary card is issued with instructions before discharge from the site.

At V3 (Day 14), the diary card is collected and reviewed. Adverse events and CM are reviewed and recorded. Vital signs are taken and symptom-directed physical examination is performed as necessary. Blood samples for safety and immunogenicity (please refer to type of tests in Table 4) are drawn.

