At V4 (Day 28), the AEs and CM are reviewed and recorded. Vital signs are taken. Eye and symptom-directed physical examinations are performed. Refer to Table 3 for eye examination method required at V4. Before the vaccinations, blood samples for safety and immunogenicity determination (please refer to type of tests in Table 4) are drawn, and urine for pregnancy and ocular samples are taken. The subjects receive the 2nd IM vaccinations together with ID or TO vaccination as specified in the Figure 1. In the event that the first TO vaccinations are planned for several subjects on the same day, there should be a minimum of two hours between the TO dosing for each subject. The two hour lagging between the TO doses should be performed for the first five subjects receiving TO doses and can be discontinued after the first these five subjects if there are no safety concerns. The subjects are observed for any immediate AE for 60 minutes after the vaccination. The diary card is issued with instructions before discharge from the site.

At V5 (Day 42), the diary card is collected and reviewed, AEs and CM are reviewed and recorded. Vital signs and ocular samples are taken. Eye and symptom-directed physical examination are performed. Refer to Table 3 for eye examination method required at V5. Blood samples for safety and immunogenicity (please refer to type of tests in Table 4) are drawn.

At V6 (Day 56), the AEs and CM are recorded. Eye and symptom-directed physical examination are performed. Refer to Table 3 for eye examination method required at V6. Blood samples for immunogenicity determination are drawn (please refer to type of tests in Table 4). Ocular sample is taken.

At V7 (Day 112), the AEs and CM are recorded. Vital signs are taken. Eye and symptom-directed physical examinations are performed. Refer to Table 3 for eye examination method required at V7. Before the vaccinations, blood samples for safety and immunogenicity determination (please refer to type of tests in Table 4) are drawn, and urine for pregnancy and ocular samples are taken. The subjects receive the 3rd IM vaccinations together with ID or TO vaccination as specified in the Figure 1. The subjects are observed for any immediate AE for 60 minutes after the vaccination. The diary card is issued with instructions before discharge from the site.

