8.9 Contraindications

8.9.1 Temporary contraindications

The below conditions (events) are considered temporary contraindications to the trial products and are assessed before each vaccination is administered.

- Oral temperature $> 38.3^{\circ}\text{C}$ measured immediately before each vaccination
- Acute illness as judged by the investigator
- Antipyretics used on the day of vaccination
- Systemic treatment with immunosuppressive agents
- Ongoing conjunctivitis or similar on the day of TO administration

If the subject is experiencing one of the above conditions, the vaccination must be postponed until he/she has recovered. On the rescheduled visit, the subject should be checked for the above temporary contraindications. If the subject is found to be eligible, the vaccine can be administered while maintaining the planned intervals.

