single urine PCR tests for *C. Trachoma* and gonorrhoea; blood pressure, heart rate and oral temperature; taken pre-vaccination when scheduled at vaccination visits (V2, V4, V7 and V9); Safety lab: renal urea and electrolytes (sodium, potassium, chloride, urea, and creatinine); liver function tests (alanine aminotransferase, alkaline phosphatase, total bilirubin, total protein, albumin); full blood count (WBC, lymphocytes, monocytes, eosinophils, neutrophils, basophils, RBC, HGB, 'HCT, and platelets); total blood for safety: approximately 13 ml; total blood for safety: approximately 8 ml; amount of blood: approximately 1 x 10 ml; amount of blood in heparin tubes: 5 x 6 ml; amount of blood in heparin tubes: 2 x 6 ml

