### 3.2.1 Treatment labels

The cohort labels will be used as treatment labels in tables, figures, and listings as described in Table 2. Cohorts who had the same treatment at first, second and/or third vaccination will when relevant be grouped at timepoints where the treatments received were similar, and will be labelled accordingly:

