**Table 2: Treatment labels**

Day and treatment	Cohort	Label
Day 0		
85 µg IM CTH522-CAF01	A1, A2, B1, B2, C1, C2	Cohort A-C CTH-01-all
15 µg IM CTH522-CAF01	D1, D2	Cohort D CTH-01-low
85 µg IM CTH522-CAF09b	E1, E2	Cohort E CTH-09
IM Placebo	F1, F2	Cohort F Placebo
Day 28 and 112		
85 µg IM CTH522-CAF01 + ID Placebo	A1	Cohort A1 CTH-01+ID-PCB
85 µg IM CTH522-CAF01 + TO Placebo	A2	Cohort A2 CTH-01+TO-PCB
85 µg IM CTH522-CAF01 + TO CTH522	B1, B2	Cohort B CTH-01+TO
85 µg IM CTH522-CAF01 + ID CTH522	C1, C2	Cohort C CTH-01+ID
15 µg IM CTH522-CAF01 + TO Placebo	D1	Cohort D1 CTH-01-low+TO-PCB
15 µg IM CTH522-CAF01 + ID Placebo	D2	Cohort D2 CTH-01-low+ID-PCB
85 µg IM CTH522-CAF09b + TO Placebo	E1	Cohort E1 CTH-09+TO-PCB
85 µg IM CTH522-CAF09b + ID Placebo	E2	Cohort E2 CTH-09+ID-PCB
IM Placebo + TO Placebo	F1	Cohort F1 Placebo+TO-PBO
IM Placebo + ID Placebo	F2	Cohort F2

Placebo+ID-PCB		
Day 140		
85 µg IM CTH522-CAF01 + ID Placebo + TO Placebo	A1	Cohort A1 CTH-01+ID-PCB+TO-PCB
85 µg IM CTH522-CAF01 + TO Placebo + TO CTH522	A2	Cohort A2 CTH-01+TO-PCB+TO
85 µg IM CTH522-CAF01 + TO CTH522 + TO Placebo	B1	Cohort B1 CTH-01+TO+TO-PCB
85 µg IM CTH522-CAF01 + TO CTH522	B2	Cohort B2 CTH-01+TO
85 µg IM CTH522-CAF01 + ID CTH522 + TO placebo	C1	Cohort C1 CTH-01+ID+TO-PCB
85 µg IM CTH522-CAF01 + ID CTH522 + TO CTH522	C2	Cohort C2 CTH-01+ID+TO
15 µg IM CTH522-CAF01 + TO Placebo	D1	Cohort D1 CTH-01-low+TO-PCB
15 µg IM CTH522-CAF01 + ID Placebo + TO CTH522	D2	Cohort D2 CTH-01-low+ID-PCB+TO
85 µg IM CTH522-CAF09b + TO Placebo	E1	Cohort E1 CTH-09+TO-PCB
85 µg IM CTH522-CAF09b + ID Placebo + TO CTH522	E2	Cohort E2 CTH-09+ID-PCB+TO
IM Placebo + TO Placebo	F1	Cohort F1 Placebo+TO-PCB
IM Placebo + ID Placebo + TO Placebo	F2	Cohort F2 Placebo+ID-PCB+TO-PCB

The full treatment will be explained in footnotes. In the above CTH-01 is an abbreviation for CTH522-CAF01, and CTH-09 for CTH522-CAF09b.

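### The SAP rule that fills a missing scheduled assessment from the next unscheduled visit has no dose limit, so at a vaccination visit a post-vaccination reading can appear in a pre-vaccination row (minor)

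*SAP*

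**What the plan says.** **The fill rule.** SAP 5.1 uses the scheduled assessment when there is one; "otherwise the first unscheduled visit succeeding the scheduled visit in question is used". It sets no limit by dose, by visit window or by the next scheduled visit.

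**Baseline.** The same section defines baseline as the last available assessment before the first administration.

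**Timing at vaccination visits.** Footnote 2 of SAP Table 1, repeated under Protocol Table 3, covers blood pressure, heart rate and oral temperature, which are "taken pre-vaccination when scheduled at vaccination visits (V2, V4, V7 and V9". Blood follows the same order in Protocol 8.2. At V2 the text reads "Before the 1st IM vaccination, blood samples for safety and immunogenicity determination"; at V4, V7 and V9 it reads "Before the vaccinations, blood samples for safety and immunogenicity determination".

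**Temperature and postponement.** Protocol 8.9.1 has oral temperature "measured immediately before each vaccination". If a temporary contraindication is present, "the vaccination must be postponed until he/she has recovered".

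**Outputs.** SAP 7.2.2 summarises vital signs by visit, with change from baseline and boxplots, and lists all data. SAP 7.2.3 only lists laboratory information. SAP 7.3.1 summarises IgG titre by visit and runs Wilcoxon tests at Day 28 and Day 126.

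**Grouping.** SAP 5 presents results by A1 to F2 unless stated otherwise. SAP 3.2.1 adds that cohorts "will when relevant be grouped at timepoints where the treatments received were similar", for example the Day 0 label "Cohort A-C CTH-01-all".

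**The concern.** A by-visit row for V2, V4, V7 or V9 is read as the state of the subject just before the dose. The fill rule can place in that row a reading taken after the dose, and nothing in the table would show it. Protocol section 10 mentions unscheduled investigation in connection with working up an adverse event, so a substitute might come from a subject who is unwell. In a trial whose primary objective is safety, a post-dose reading shown as pre-dose would blur the before-and-after comparison that the vital-sign tables exist to give.

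**Working it through.** The plan gives no figure to reproduce. The check sets the rule against the schedule and the outputs, followed by one line of arithmetic.

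**1. Is there a limit elsewhere?** I found none in either document. The baseline definition is tied to the first dose, but it governs the baseline value and not the by-visit rows. The statements in SAP 5.1 and 7.6 that nothing is imputed do not help, because the substitute is an observed value, only assigned to another timepoint.

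**2. Order of events at a dosing visit.** Vital signs come first, then the vaccination, then any unscheduled visit that succeeds the scheduled one. For a subject dosed at that visit, the substitute is necessarily post-dose. Vital signs are scheduled at 11 visits (all except V6), and 4 of these 11 are vaccination visits. The exception is a postponed dose: if the rescheduled visit is recorded as unscheduled, its reading can still be pre-dose.

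**3. Which outputs are exposed?**

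| Output | Exposure |
|---|---|
| Heart rate and blood pressure by visit, change from baseline, boxplots (SAP 7.2.2) | Exposed; descriptive only |
| Oral temperature by visit | Less exposed, since it is checked before every dose (Protocol 8.9.1) |
| Baseline value | Protected by its own definition; if V2 is missing, it falls back to an earlier pre-dose value |
| Safety laboratory values (SAP 7.2.3) | No by-visit numerical summary |
| IgG titre, Day 28 and Day 126 tests (SAP 7.3.1) | Only if an unscheduled IgG sample exists; none is planned |

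**4. Can the rule cross a later dose?** On one reading of *succeeding*, the rule looks past the next scheduled visit. From Table 1, V8 is V7 + 12 to 16 days and V9 is V7 + 26 to 30 days. The Day 140 dose therefore falls between 26 − 16 = 10 and 30 − 12 = 18 days after V8. A missing Day 126 value could then be filled from a visit after the Day 140 dose. On the other reading, which stops at the next scheduled visit, it could not.

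**5. Size of one substitution.** Let d be the substituted value minus the missing pre-dose value, and n the number of subjects in the row. The group mean moves by d/n. Mean change from baseline moves by the same amount, because baseline is untouched.

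The documents give no d, and the figure with the group sizes is not shown. Assumptions:
- d between 0 and 30 bpm for heart rate.
- Equal allocation. Protocol 11.4.3 gives 91% active: 66 × 0.91 ≈ 60 subjects. Over the 10 active groups A1 to E2, n = 60/10 = 6.

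Results:
- By single group: 0/6 = 0 to 30/6 = 5 bpm.
- Where A to C are pooled under SAP 3.2.1: n = 6 × 6 = 36, giving 0 to 30/36 ≈ 0.8 bpm.

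**The case against.** The strongest reply is that the situation will hardly ever arise. The subject must attend, be dosed, lack a heart-rate or blood-pressure reading, and then return for an unscheduled visit at which that sign is measured. If the whole visit is missed, no dose is given there. The three vital signs are scheduled together, and temperature is checked before every dose, so a lone missing heart rate would be an isolated omission. Protocol section 10 names laboratory testing and other investigations for an adverse event, without naming vital signs. The exposed outputs are descriptive, all data are listed, and clinically significant findings are recorded as adverse events.

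All of this stands, and it limits the practical reach. It does not remove the defect: whenever the rule is used in a subject dosed at the visit, it gives a value on the wrong side of the dose.

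A reader might infer more, and the documents do not support it:
- **Contaminated baseline or Day 28 tests.** The baseline definition excludes post-dose values, and no unscheduled IgG sample is planned.
- **A systematic rise in the vital-sign means.** No document gives an excess. A reading taken at an unscheduled visit may be ordinary, so the range must include zero.
- **Day 126 values certainly drawn from after Day 140.** This rests on one of two available readings of *succeeding*.

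**Conclusion.** The point holds, as a minor one. As written, SAP 5.1 lets a post-vaccination vital-sign reading stand in the pre-vaccination row of V2, V4, V7 or V9 for a subject dosed at that visit, unless the dose was postponed and the substitute precedes it. In practice the exposure is confined to descriptive heart-rate and blood-pressure summaries and boxplots; the Fisher tests on solicited reactions do not use these rows.

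Neither the frequency nor the size can be estimated from the documents. The effect of one substitution is d/n, and it is zero if the rule is not invoked or the reading is ordinary. The 0 to 5 bpm figure illustrates scale only, and rests on an assumed difference of 0 to 30 bpm and an assumed n of 6. The possible reach past a later dose is an ambiguity to close, not an established error.

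**What to change.** Amend SAP 5.1 to read:

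> If a scheduled assessment is missing, the first succeeding unscheduled assessment is used only if it was taken before the next scheduled visit (where there is one) and (a) for V2, V4, V7 and V9, before the vaccination belonging to that visit if given, including a postponed vaccination, or (b) for other visits, before the next vaccination (where there is one); otherwise the value is missing.

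Where clock times are not recorded, treat an unscheduled visit that follows the dosing visit as post-dose. Do not also require the reading to lie inside the Table 1 window, so that genuine pre-dose readings from postponed visits are kept.

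The cost is one sentence in the SAP, a small check in the derivation program, and a few values left missing, which fits the SAP's observed-case approach. No trial procedure changes.

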## 5.2 Subject Disposition

An overall summary table of the subject disposition will be prepared with number of subjects in the following categories and sub-categories:

- Screened subjects
  - Screening failures
  - Not assigned
  - Randomised
- Analysis sets
  - SAF
  - FAS
  - PP population
- Completers
- Withdrawals with reason:
  - Adverse event
  - Screen failure
  - Withdrawal by subject
  - Lost to follow-up
  - Pregnancy
  - Death
  - Protocol violation
  - Investigator decision
  - Sponsor request
  - Other

All information will be listed.

## 5.3 Protocol Deviations

Protocol deviations consist of the types

- Inclusion/Exclusion criteria
- Prohibited Medication
- Visit out of window
- Lab
- Other

and will be categorised before unblinding of the trial as major or minor, and those leading to exclusion from PP population will be identified and documented.

Protocol deviations will be summarised for all randomised subjects by category and type. Covid-19 related deviations are identified before DBL and will be summarised by category.

All deviations will be listed.

## 5.4 Baseline Characteristics and Demographics

Baseline characteristics and demographics consist of age, gender, race, weight, height, and BMI.

Demographics will be summarized using descriptive statistics. Age and gender will in addition be summarised for FAS and PP.

All information will be listed.

## 5.5 Medical History

Medical history will be summarised by system organ class (SOC) and preferred term (PT).

All information will be listed.

# 6 Exposure and Other Dosing Information

## 6.1 Exposure

Number of vaccinations according to protocol will be summarised by type

- Intramuscular (IM)
- Intradermal (ID)
- Topical ocular (TO)

and by content

[figure not shown]
- CTH522
- Placebo

Treatment exposure is assessed by time from first vaccination to end of trial and will be summarised in days.

All data will be listed.

## 6.2 Prior and concomitant medication

Medications stopped before first treatment with IMP is entitled prior medication, and other medications concomitant medication. The medications are coded using WHO Drug DDE – Sep 2019 and both will be summarised by ATC level 3 and drug name and will also listed by subject.

## 7 Statistical Methodology for Primary and Secondary Endpoints

### 7.1 Analysis and Presentation of the co-Primary Safety Endpoints

The co-primary endpoints are:

- Solicited local injection site reactions after ID and/or IM administration of the vaccines: erythema, pruritus, pain, tenderness, swelling, and warmth occurring up to and including 14 days after any IMP administration
- Solicited local reactions after TO administration of the vaccine: watering eyes, swelling of eyelid, eye redness, and eye discomfort occurring up to and including 14 days after any IMP administration
- Solicited systemic reactions after IM and/or ID administration of the vaccines: oral temperature  $> 38.3^{\circ}\text{C}$ , chills, myalgia, and rash occurring up to and including 14 days after any IMP administration
- Any other adverse events (AEs)

These are collected in the subjects' diaries.

The primary analyses will be carried out for the SAF.

AEs will be coded using the Medical Dictionary for Regulatory Activities (MedDRA) version 22.1 - Sep 2019. AEs will be regarded as treatment emergent AEs (TEAEs) if they occur after administration of randomised treatment.

Only TEAEs will be summarised. The summaries will include number of events, number of subjects, and proportion of subjects reporting these events.

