8.7 Safety assessments

The trial staff must record all AEs, non-serious and serious, expected and unexpected in the relevant form of the eCRF. This starts from the time after the subject has signed the informed consent form (ICF) at V1 until the end-of-trial at V12.

The source of AEs covers, for example, the subject's response to questions about his/her health (a standard non-leading question), information from diary card, symptoms spontaneously reported by a subject, results from pre-defined laboratory testing and examinations where the findings are assessed by the investigator to be clinically significant changes or abnormalities, and other information relating to the subject's health becoming known to the investigator (for example hospitalisation).

The subjects will remain at the site for 60 minutes after each vaccination so that any immediate AEs observed may be recorded. It is also documented if no immediate AEs occurred. Trial staff will ensure that the subjects have a diary card, ruler to measure and thermometer to enable them to record AEs while away from the clinical site.

From the day of vaccination until seven days later, solicited AEs and unsolicited AEs will be recorded through the use of diary cards. Between Day 7–14, the subject will be asked to fill in details in the diary *only* if they experience an AE or if any medications were taken.

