10.1 Standard recording and assessment of adverse events

10.1.1 Collection and recording of AEs

The source of AEs covers, for example, the subject's response to questions about his/her health (a standard non-leading question), information from diary card, symptoms spontaneously reported by a subject, investigations and examinations where the findings are assessed by investigator to be clinically significant changes or abnormalities, other information relating to the subject's health becoming known to the investigator (for example hospitalisation).

Safety data are collected according to the timeframe specified in the flow chart (Table 3). The solicited AEs listed below will be collected via the diary cards:

- Solicited local injection site reactions after ID and/or IM administration of the vaccines: erythema, pruritus, pain, tenderness, swelling, and warmth
- Solicited ocular reactions after TO administration of the vaccine: watering eyes, swelling of eyelid, eye redness, and eye discomfort
- Solicited systemic reactions after IM and/or ID administration of the vaccines: oral temperature $> 38.3^{\circ}\text{C}$, chills, myalgia and rash
- Any other AEs

The investigator or delegated staff must record all AEs, non-serious and serious, expected and unexpected in the relevant form of the eCRF.

The date of onset is the date when the first sign(s) or symptoms were first noted. If the AE is an abnormal clinically significant laboratory test or outcome of an examination the onset date is the date the sample was taken or the examination was performed.

If an AE or SAE is still ongoing or the outcome is unknown at the end of the trial (at the subject's last visit), it must be followed up by the investigator/delegate until it has been resolved or stabilised.

All SAEs must be recorded on the Serious Adverse Event form in the eCRF. If the investigator has unblinded the trial drug allocation of the subject, the screen-dump from the unblinding is forwarded together with the completed Serious Adverse Event (SAE) form to SSI (please see Section 5 for contact information).

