#### 7.1.4 Any other AEs

Any other AEs are all TEAEs not included in the above three sections.

The number and percentage of subjects and the number of events will be presented by system organ class (SOC) and preferred term (PT) for the following timespans:

- From Day 0 vaccination to before Day 28 vaccination for the four treatment regimens present
  - Cohort A-C
  - Cohort D
  - Cohort E
  - Cohort F
- From Day 28 vaccination to before Day 112 vaccination and
- From Day 112 vaccination to before Day 140 vaccination

The immediate above two tables will include the nine treatment regimens present, where the placebo cohort (F) will be regarded as one

- Cohort A1
  - Cohort A2
  - Cohort B
  - Cohort C
  - Cohort D1
  - Cohort D2
  - Cohort E1
  - Cohort E2
  - Cohort F
- From Day 140 vaccination to end of trial for the 11 treatment regimens present, where the placebo cohort (F) will be regarded as one
  - Cohort A1
  - Cohort A2
  - Cohort B1
  - Cohort B2
  - Cohort C1
  - Cohort C2
  - Cohort D1
  - Cohort D2
  - Cohort E1
  - Cohort E2
  - Cohort F

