### 7.2.1 Adverse Events

The summaries will include number of events, number of subjects, and proportion of subjects reporting these events.

Certain, probable, or possible related AEs are defined as Adverse Drug Reactions (ADRs).

An overall summary table will include summary of TEAEs, TESAEs, Fatal AEs, ADRs, AEs leading to drug withdrawal, drug interruption, or leading to withdrawal from trial, AEs by severity, AEs by relationship, AEs by outcome, and ADRs by severity.

A summary by SOC and PT will be presented for:

- TEAEs
- Serious Adverse Events (SAEs)

- TEAEs by severity (mild, moderate, severe, potentially life-threatening)
- TEAEs by relationship (Certain, probable, possible, not related)
- ADRs by severity
- TEAEs leading to drug interrupted
- TEAEs leading to drug withdrawn
- TEAEs leading to withdrawal

Listings will be made of all AEs, including non-TEAEs, SAEs, clinically significant AEs, ADRs including Suspected Unexpected Serious Adverse Reaction (SUSARs), and TEAEs leading to drug interruption or withdrawal from treatment.

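### The TEAE definition has no clause for worsening, so an AE ongoing at Day 0 that worsens after vaccination can drop out of the TEAE-based summaries

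*SAP*

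**What the plan says.** Protocol 8.7 sets the AE recording period: "This starts from the time after the subject has signed the informed consent form (ICF) at V1 until the end-of-trial at V12". The V1 window is Day -90 to -1, so AEs that begin before the first dose enter the database.

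Protocol 10.1.1 fixes the start of an event: "The date of onset is the date when the first sign(s) or symptoms were first noted". For a clinically significant laboratory or examination finding, the date is that of the sample or examination. Nothing is said about a later rise in intensity.

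SAP 7.1 then defines treatment emergence: "AEs will be regarded as treatment emergent AEs (TEAEs) if they occur after administration of randomised treatment". The next paragraph adds: "Only TEAEs will be summarised". SAP 7.1.4 builds the fourth co-primary endpoint on the same class: "Any other AEs are all TEAEs not included in the above three sections".

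SAP 7.2.1 covers the other AE outputs. Its tables by system organ class and preferred term are mostly labelled TEAEs, but the SAE table, the ADR table and several rows of the overall summary (fatal AEs, ADRs, AEs by severity, relationship and outcome) carry no such label. ADRs are defined there on AEs, not on TEAEs. On listings it says: "Listings will be made of all AEs, including non-TEAEs, SAEs, clinically significant AEs, ADRs".

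**The concern.** A vaccine can aggravate something that is already there. The usual way to capture this is to count as treatment-emergent both events that start after dosing and events that start earlier and worsen afterwards. The SAP has only the first half. Because the protocol ties onset to the first symptom, a worsened event keeps its pre-dose date and falls on the wrong side of the definition.

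Safety is the primary objective, and AE frequencies are the main product of the trial. Leaving such an event out can only lower the reported frequency or severity in the group concerned. The groups are small, so a single subject shows in the percentages.

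**Working it through.** **Tracing an event through the rules.** Take a hypothetical mild headache first noted between V1 and Day 0, still present at the first vaccination, and severe some days later.

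1. It is recorded, because collection starts at consent (Protocol 8.7).
2. Its onset is the date it was first noted, which is before the first dose (Protocol 10.1.1).
3. With that onset it did not occur after administration, so it is not a TEAE (SAP 7.1).
4. It is not summarised under SAP 7.1, and it is outside the fourth co-primary endpoint, which takes TEAEs only (SAP 7.1.4).
5. It appears in the listing of all AEs, which includes non-TEAEs (SAP 7.2.1).
6. Whether it also reaches the overall AEs-by-severity rows, or the ADR table if judged related, depends on whether the restriction in 7.1 carries into 7.2.1. The SAP does not say.

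**Looking for a rule that would rescue it.** The AE definitions and assessments (Protocol 10 and 10.1.2), the co-primary endpoint sections (SAP 7.1.1 to 7.1.4), missing values (SAP 7.6) and deviations from protocol (SAP 8) were checked. None counts worsening as treatment-emergent, and none requires worsening to be entered as a new AE. Step 3 would fail only if a site chose to open a new record with a post-dose onset.

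**Size of one omitted subject.** The plan gives no figure to reproduce and no rate of AEs ongoing at Day 0, so the number of affected subjects cannot be computed. What can be shown is the weight of one subject.

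Inputs: 66 subjects in six cohorts (Protocol 8.1); 9% on placebo only and 91% active (Protocol 11.4.3). The group sizes stand in Figure 1, which the text available here does not show. Equal active cohorts, split into equal subgroups, are therefore an assumption.

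- Placebo cohort F: 0.09 × 66 = 5.94, so 6
- Active: 66 − 6 = 60; per cohort 60 / 5 = 12; per subgroup 12 / 2 = 6
- Pooled A-C: 3 × 12 = 36

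Change in a reported percentage from one subject = 100 / n. The columns are those of SAP 7.1.4:

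| Period | Column | n | Points per subject |
|---|---|---|---|
| Day 0 to before Day 28 | A-C pooled | 36 | 2.8 |
| | D or E | 12 | 8.3 |
| | F pooled | 6 | 16.7 |
| Day 28 to before Day 112, and Day 112 to before Day 140 | B or C | 12 | 8.3 |
| | A1, A2, D1, D2, E1, E2, or F pooled | 6 | 16.7 |
| Day 140 to end of trial | each active subgroup, or F pooled | 6 | 16.7 |

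**The case against.** **The event may not be lost from every summary.** A reader might infer that a worsened pre-dose event is absent from all AE tables. The documents do not support that. The restrictive sentence sits in the co-primary section, while 7.2.1 names SAE, ADR and severity outputs without the treatment-emergent label. A serious or related event could appear there. This stands. What is shown is exclusion from the TEAE-based tables and an ambiguity about the rest.

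**Worsening could be a new AE.** The SAP speaks of events that occur after dosing, and the AE definition in Protocol 10 is wide enough to cover a post-dose worsening as an event in itself. A site that records it so closes the gap. This also stands as a possibility, but no text makes it the rule, so the result depends on local habit.

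**Few events can qualify.** The AE must still be ongoing at Day 0. Exclusion criteria EX3 and EX11 remove significant active disease, clinically significant laboratory abnormalities and evident ocular disease. Protocol 8.9.1 and 9.9 postpone vaccination for acute illness, fever or recent antipyretics or analgesics. Injection site reactions cannot precede the first injection. A laboratory value that first becomes clinically significant after dosing takes a post-dose date and is a TEAE. All this stands and makes the affected pool small. It does not remove mild symptoms that meet none of these criteria.

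**The arms are treated alike.** A reader might infer that the rule favours the vaccine in comparisons. The same definition applies to placebo and active subjects in a blinded trial, so only understated absolute rates can be claimed.

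**The size is easily overstated.** A reader might take one in three (33 points) for F1, assuming three subjects there. That does not apply to the tables for other AEs, where SAP 7.1.4 shows cohort F as one group. Setting the 90-day pre-dose window against the 238 days after dosing does not help either, because only AEs ongoing at Day 0 matter.

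**Nothing is hidden.** Non-TEAEs are listed, and SAEs go on their own form with reporting within 24 hours (Protocol 10.1.1 and 10.2). That is correct, but a listing gives no group rate.

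**Conclusion.** The point holds in a limited form. Read with Protocol 10.1.1, SAP 7.1 leaves an AE that starts between consent and the first dose, persists at Day 0 and worsens after vaccination out of the TEAE-based summaries, including the co-primary tables of other AEs. A listing is its only assured place. This rests on one assumption: that the worsening is not entered as a new AE. It is unclear whether the SAE, ADR and severity outputs of 7.2.1 share the restriction.

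The consequence is a possible understatement of absolute AE rates in any arm, not a known bias between arms. The number affected cannot be derived and is probably small. With equal group sizes assumed, one subject is worth between 2.8 and 16.7 percentage points in the Day 0 to Day 28 table. This is a cheap improvement to a primary-objective definition, not a defect that puts the trial's safety conclusions in doubt.

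**What to change.** In SAP 7.1, define a TEAE as an AE with onset after the first IMP administration, or with earlier onset and an increase in grade (on the scale the protocol already uses) or in seriousness after it. Then:

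- assign a worsened event to the vaccination period in which it worsened;
- state that the same definition governs the SAE, ADR and severity outputs in SAP 7.2.1;
- state how a worsening is recorded in the eCRF, so that the result does not depend on site habit;
- identify the cases among AEs ongoing at Day 0 at the data review meeting that SAP 2 and 4 already place before unblinding;
- note the change in SAP 8.

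The cost is a few sentences and a short blinded review of the AEs ongoing at Day 0. Reported AE rates may become slightly less favourable.
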